Aim 1: Adapt a previously validated machine learning algorithm to predict risk of colorectal cancer or adenoma among a retrospective cohort of Penn Medicine patients living in vulnerable zip codes within Philadelphia County. We will improve upon a previously validated machine learning algorithm¹ to predict risk of colorectal cancer by (1) re-training the model to predict both cancer and adenoma detection; (2) integrating additional clinical and socioeconomic risk factors for colorectal cancer risk; and (3) retraining the model in a cohort of individuals living in Philadelphia County zip codes that are minority-predominant and have lowest median incomes in the county. We will compare algorithm performance to existing criteria, based on age and prior colon cancer screening history, which are currently used to stratify colorectal cancer risk among Penn Medicine patients. We hypothesize that machine learning models will maintain good performance in predicting CRC risk among a community living in a persistent poverty area.

Aim 2. Test the feasibility, usability, and effectiveness of algorithm-informed navigation on colorectal cancer screening rates and adenoma detection rates among Penn Internal Medicine and Family Medicine patients residing in racially and ethnically diverse zip codes. We will use the machine learning algorithm developed in Aim 1 to inform the CRC screening navigation program process and evaluate its impact on the identification of Penn Internal Medicine and Family Medicine patients with adenomas and CRC. We will generate automated monthly lists of Penn Medicine Internal and Family Medicine patients from diverse communities ranked by predicted cancer risk. High-risk patients will be prioritized for navigation of socioeconomic and financial barriers to colonoscopy through an existing navigation program created and managed by our team at the University of Pennsylvania.² In addition to assessing feasibility and usability, we will evaluate the effectiveness of the program on rates of completed colonoscopies and rates of CRC/adenoma detection, compared to historical rates prior to the intervention. We hypothesize that algorithm-informed navigation will improve CRC screening rates and cancer/adenoma detection rates.

Need for Cancer Control Program in Philadelphia County

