adenoma detection rate (40%). An adenoma detection rate of 40% is an increase of at least 15 percentage points, or a 60% increase, over the national benchmark of 15% to 25%.

Patients and clinics served: Currently the On July 1, 2015, the program was enlarged and institutionalized by Penn Medicine with expansion from 5 to 11 zip codes to include Southwest and South Philadelphia. On January 1, 2021, the program expanded from 11 to 18 zip codes throughout Philadelphia County. Currently patients receiving care at one of 4 Internal Medicine practices located in Philadelphia County participate in the program. Another key goal of Penn Medicine is to expand navigation services beyond Internal Medicine to other types of primary care practices, including 3 Family Medicine practices in Philadelphia County. **As part of the resulting expansion of patients requiring navigation, additional FTE navigation staff will be needed and are requested as part of this Administrative Supplement.** Additionally, a key challenge in scaling this navigation program is identifying patient populations at increased risk of CRC, who may benefit most from timely navigation. While risk stratification guidelines exist to determine who should be prioritized for colonoscopy¹⁰, these require time-consuming chart review and may not be adequately sensitive. Automated machine learning algorithms based on routine EHR data accurately estimate a patient's relative risk of CRC in multi-institutional studies.^{1,11,12}

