The focus group will garner feedback about the intervention and strategies to integrate automated navigation services into routine workflow. This intervention will occur without physician referral; however, given that some automated predictions may be incorrect, we will display results from an algorithm that predicts both CRC and adenoma vs. a model that predicts CRC alone. We will elicit perspectives from these clinic groups about which algorithm they agree with the most, in order to determine which algorithm to proceed with for Aim 2.

PDSA cycles: After training the algorithm, we will conduct a 3-month pilot using patients from one primary care practice, using the Plan-Do-Study-Act (PDSA) Framework¹³ to identify patient and clinic barriers to this research program. In the “Plan” stage, the critical elements are: (1) integrating flags for algorithm-predicted high-risk patients into existing automated lists given to the navigator program; (2) selection, training and defining the functions of the new CRC screening navigator; and (3) establishment of a network of clinic partners serving patients in the high poverty navigation program. The “Do” stage is focused on the implementation of an algorithm-facilitated navigation process to address the clinical and social barriers to CRC screening. The “Study” stage is defined by tracking enrolled patients and evaluating program measures that include completion of screening and adenoma detection rates and, then, in the “Act” stage, optimizing the program to expand the reach of the program to serve a broader population of patients, potentially even outside of Penn Medicine.

Approach

Aim 1. Validation of ML algorithm to predict colon cancer and adenoma risk

Study Design. Retrospective cohort study

Cohort. 60,270 unique patients without a prior CRC diagnosis who had a colonoscopy order placed by a Penn Internal Medicine or Family Medicine provider living in one of 18 minority-predominant zip codes in Western and Southwestern Philadelphia County; completed a colonoscopy at Penn between January 1st, 2010 and December 31st, 2019; and were seen by a Penn primary care physician in the preceding year. We will split the cohort into training (70%) and validation (30%) sets at the patient-level so that patients are represented in either the training or validation set only.

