Cohort. The cohort will consist of patients residing in 18 zip codes in Western and Southwestern Philadelphia who have primary care providers in 4 Penn Medicine Internal Medicine practices and 3 Penn Medicine Family Medicine Practices. Patients will have had a colonoscopy order placed in the past 6 months and have not scheduled, cancelled, or no-showed to their colonoscopy.

Intervention. This intervention will utilize the existing Penn Medicine CRC patient navigation program; administrative supplement funding will be used to expand the staff from 1.5 FTE to 2.5 FTE. In the revised intervention, we will provide a monthly list of ~300 patients with unfilled colonoscopies, risk-stratified according

Program Director/Principal Investigator (Last, First, Middle): [name]

the ML algorithm and select high-risk criteria.¹⁰ The navigation team will prioritize timely outreach and navigation to high-risk patients according to a script that communicates risk.

Outcome. The co-primary outcomes, measured within 3 months of enrollment, will be (1) enrollment in navigator program (feasibility); (2) completion of colonoscopy or FIT testing; and (3) adenoma detection rate.

Analysis Plan. We will use an intention-to-treat analysis. We will use propensity score matching using clinical and sociodemographic characteristics to create matched cohorts of patients between the intervention participants and historical controls from the same clinics in the year prior. We will then use logistic regression to assess the association between the intervention and the two primary outcomes, adjusted for age, gender, comorbidity, and area-level socioeconomic status.

Statistical Power. A sample of 344 participants (172 per group) will provide >90% power, assuming Type I error rate with a 2-sided α 0.05 and 50% dropout/refusal to participate to navigation, to detect a 20 percentage-point (pp) increase in colon cancer screening completion (40 \rightarrow 60%, SD 20%) in the intervention group.

Work plan and timeline

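### Aim 2's before-after contrast cannot separate the algorithm from the added navigator FTE, the risk script and first-time navigation in three Family Medicine practices

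*Combined protocol and SAP*

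**What the plan says.** **Before the intervention.** Under Existing Services, a navigation program with 1.5 FTE already serves patients of four Internal Medicine practices. Its eligibility rule (a colonoscopy ordered within six months and not carried through) is the one Aim 2 uses. The plan wants to bring in three Family Medicine practices and, because more patients will then need navigation, says that "additional FTE navigation staff will be needed and are requested as part of this Administrative Supplement".

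**What changes.** Under PDSA cycles, the same planning stage covers "integrating flags for algorithm-predicted high-risk patients into existing automated lists given to the navigator program" and "selection, training and defining the functions of the new CRC screening navigator". In Aim 2, Intervention, "administrative supplement funding will be used to expand the staff from 1.5 FTE to 2.5 FTE". There, "we will provide a monthly list of ~300 patients with unfilled colonoscopies", stratified by the algorithm together with selected high-risk criteria, and "The navigation team will prioritize timely outreach and navigation to high-risk patients according to a script that communicates risk". Specific Aims describes the lists as "ranked by predicted cancer risk".

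**How it is judged.** Three co-primary outcomes are measured within 3 months: enrollment in navigation, completed colonoscopy or FIT, and adenoma detection. Controls are propensity-matched patients of the same clinics in the preceding year. The logistic model adjusts for age, gender, comorbidity and area-level socioeconomic status. The stated expectation is: "We hypothesize that algorithm-informed navigation will improve CRC screening rates and cancer/adenoma detection rates". Work plan and timeline then presents the study as preliminary data for a cluster-randomized trial of ML-guided navigation.

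**The concern.** The hypothesis names the algorithm, but the contrast compares two periods that differ in several ways at once. By the plan's own description the algorithm flags and ranks patients on lists that already exist; it does not change who is eligible. Extra navigator time and a first offer of navigation can also raise screening completion, with no help from ranking. If a gain is reported as an effect of algorithm-informed navigation, the follow-on trial may be justified and sized on an effect that came from staffing or from extending the service to new practices.

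**Working it through.** **1. The plan's own figure.** Inputs from Statistical Power: 172 per group, 40% versus 60%, two-sided α 0.05. The pooled proportion is 0.50.

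- SE under no difference: √(2 × 0.25/172) = 0.0539
- SE under the alternative: √((0.24 + 0.24)/172) = 0.0528
- z = (0.20 − 1.96 × 0.0539)/0.0528 = 1.79, giving power of 96.3%

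The claim of more than 90% is reproduced if all 172 per group are analysed at the full 20-point effect. The point here does not depend on it: power concerns detecting a difference, not what caused it.

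**2. What differs between the compared groups.**

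| Component | Prior year, 4 Internal Medicine practices | Prior year, 3 Family Medicine practices | Intervention period, all 7 |
|---|---|---|---|
| Navigation program | yes | not in program | yes |
| Navigator FTE | 1.5 | not in program | 2.5, shared |
| ML-ranked list | no | no | yes |
| Script communicating risk | not stated | not in program | yes |

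Within the Internal Medicine practices, FTE and ranking switch together with the period. In the Family Medicine practices, access to navigation switches as well. Matching and the four adjustment variables describe patients and their areas. They can balance who is compared, but cannot split components that depend only on period and practice. The model has one intervention term, so it returns one combined effect. The plan has no concurrent unranked list, workload covariate or component analysis.

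**3. Direction of the staffing change.**

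- Total: 2.5/1.5 = 1.67, a rise of 67%
- Per practice: 1.5/4 = 0.375 before and 2.5/7 = 0.357 after; 0.357/0.375 = 0.95, a fall of 5%

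The documents give no listed patients per FTE for the earlier period, so capacity per listed patient may have risen or fallen.

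**4. Size of the staffing effect.** Let c be the share of listed patients reached and b the completion rate if not reached. Existing Services gives completion if contacted as 0.50 × 0.80 = 0.40 (colonoscopy only).

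- Completion = 0.40c + b(1 − c)
- Change from staffing alone = Δc × (0.40 − b)

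Neither c, Δc nor b is documented. If the power statement's 40% for controls is taken at face value, 0.40 = 0.40c + b(1 − c), so b = 0.40 for any c below 1, and extra reach adds nothing. With a lower b it adds something. FIT also counts toward the outcome, so 0.40 may understate completion among those contacted. The documents therefore fix neither the sign of Δc nor the size of (0.40 − b).

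**The case against.** The strongest reply is that the plan already evaluates a package. The Intervention paragraph describes staff, list and script together, the analysis refers to the intervention as a whole, and a one-year feasibility study need not separate components. Much of this stands, and it is why the remedy is mainly wording. But the package reading is nowhere stated, and both the hypothesis and the follow-on trial name the algorithm.

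Other replies also stand in part:

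- **The added FTE is meant to absorb growth.** True, so more capacity per patient cannot be asserted. But that growth includes practices whose prior-year controls were outside the program, which is another non-algorithm explanation.
- **The script is not called new, and conveying risk may be part of algorithm-informed care.** Fair. The staffing and practice changes remain without it.
- **The outcomes are not silent on the mechanism.** A reader might infer that reach is unmeasured, or that the outcomes cannot register ranking. Neither follows. Enrollment is a partial reach measure, and adenoma detection could respond to ranking by risk. If navigators cannot reach everyone listed, ranking also affects who is called, not only when. But enrollment mixes being contacted with agreeing, and both outcomes inherit the same confounded comparison. The Analysis Plan also models two primary outcomes where three are listed.

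**Conclusion.** The limitation holds: a before-after gain in Aim 2 could be read at most as an effect of the package, with the usual limits of a historical comparison, and not of the algorithm. It does not invalidate the study, but it changes what may be concluded and is cheap to correct.

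It rests on three readings:

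- The added FTE is in place when the ranked list is used. The PDSA text and the Intervention paragraph pair them, but the text gives no start date.
- The Family Medicine practices lacked program access in the control year, as Existing Services indicates.
- The algorithm reorders an existing list, since the eligibility rule is unchanged.

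No size can be attached. A reader might infer that staffing alone delivers about half of the 20-point target. With assumed reach rising from 50% to 83.3% and assumed background completion of 10%, the gain is (0.833 − 0.50) × (0.40 − 0.10) = 10 points. The documents do not support this: those inputs imply control completion of 0.50 × 0.40 + 0.50 × 0.10 = 25%, against the plan's 40%, and they assume that capacity per patient rises in full proportion to FTE. Nor can the effect of ranking be gauged by calling every patient earlier, because reordering moves some patients later.

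**What to change.** **(a) Wording.** State in the Aim 2 hypothesis, Analysis Plan and conclusion that the before-after contrast estimates the whole package (added FTE, risk script, ML ranking and new navigation in Family Medicine), not the algorithm. Do not cite it as evidence of an algorithm effect for the follow-on trial.

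**(b) Reporting.** Give the screening contrast separately for the four already-navigated Internal Medicine practices and the three Family Medicine practices. In the Internal Medicine practices, use navigator logs for both periods, where available, to report:

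- listed patients per FTE
- share of listed patients reached
- days from listing to first contact
- completion among those reached

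These are descriptive. They show whether a gain came with more or faster calling; they do not isolate ranking. Time from listing to completed screening would not isolate it either, because added staff can shorten that interval too.

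**Cost.** The headline claim becomes narrower, the strata are smaller than the planned 172 per group, and logs must be extracted, with unknown completeness for the prior year. No new patients or arms are needed, and (a) needs no data.

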CRC risk algorithm: The Penn Predictive Healthcare Group is a Penn Medicine-employed team of data and human factors scientists. Their objective is to use EHR data to develop real-time, automated predictive models for use in inpatient and outpatient care settings to inform clinical care delivery. In collaboration with the Predictive Healthcare Group, we have adapted a previously published EHR-based ML algorithm¹ based on complete blood count records from EHR data, adding additional variables of significance including age, gender, BMI, alcohol and smoking status, and relevant comorbidities to generate a model with good discrimination (AUC 0.73), sensitivity (44%), and specificity (90%) in identifying future risk of CRC or adenoma (**see Fig. 4**). During the period of this award, the Data Science Team will retrain the algorithm in a racially and ethnically diverse subgroup residing and receiving care within Penn Medicine Internal and Family Medicine clinics located in Philadelphia County.

Strategies to Elicit Needs

Given that we are utilizing a central navigator program that exists outside of the clinic and does not require additional clinic staff, in addition to the fact that outcomes will be identified from routine EHR records and not from dedicated research staff within clinics, we do not anticipate that there will be issues implementing this program into our target clinics given our preexisting infrastructure. However, we will take several steps to ensure clinics' feedback prior to Aim 2.

Focus groups: First, to ensure buy-in and feedback of the additional clinics participating in this program, we will conduct focus groups with relevant leadership from each of the 3 new clinics and each of the 4 older clinics.

Figure 3. CRC navigator workflow

[figure not shown]
[figure not shown]

Figure 4. ML algorithm performance in unselected Penn Medicine cohort

Program Director/Principal Investigator (Last, First, Middle): [name]

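### Aim 2 ranks patients by predicted risk, but the plan does not state that historical controls are scored or put the score in the outcome model, so a changed case mix could look like better adenoma detection

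*Combined protocol and SAP*

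**What the plan says.** - **Selection by risk.** Specific Aims, Aim 2, describes monthly lists "ranked by predicted cancer risk". Under Approach, Aim 2, Intervention, "we will provide a monthly list of ~300 patients with unfilled colonoscopies, risk-stratified according" to the algorithm and to selected high-risk criteria, and "The navigation team will prioritize timely outreach and navigation to high-risk patients according to a script that communicates risk".
- **What the score predicts.** Existing Services, CRC risk algorithm, reports for the current model "sensitivity (44%), and specificity (90%) in identifying future risk of CRC or adenoma". Its inputs are blood counts plus age, gender, BMI, alcohol, smoking and comorbidities. Approach, Aim 1, adds laboratory, utilization and socioeconomic predictors for the retrained model.
- **Outcome.** The Aim 2 co-primary list ends "2) completion of colonoscopy or FIT testing; and (3) adenoma detection rate". No denominator is given for the last item. The Analysis Plan models two primary outcomes without naming them, but Specific Aims, Aim 2, says that detection will be compared with historical rates.
- **Comparator and analysis.** The analysis is by intention to treat. The comparator is "historical controls from the same clinics in the year prior". On matching, "We will use propensity score matching using clinical and sociodemographic characteristics to create matched cohorts of patients"; the characteristics are not itemised. The logistic model is "adjusted for age, gender, comorbidity, and area-level socioeconomic status".
- **Scoring of controls.** No section mentions it. Aim 1 does not fill the gap: its cohort is restricted to colonoscopies completed by the end of 2019, and the document is dated October 2021.

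**The concern.** The score decides who is reached first and is built to predict one of the outcomes. Prior-year controls were handled before the algorithm was in use. If the two groups differ in their mix of predicted risk, their adenoma yields will differ even when navigation finds no more disease at any given risk level.

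The listed covariates would absorb part of such a difference. Laboratory values, utilization, BMI, smoking and alcohol are score inputs that the outcome model does not name.

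Two undefined terms decide how much this matters: who counts as an intervention participant, and the denominator of the detection rate. At stake is the reading of a co-primary result that is meant to support an application for a cluster-randomized trial. An effect due to case mix would feed into that trial's assumptions.

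**Working it through.** **Inputs from the document**
- Sensitivity 44%, specificity 90% (Existing Services).
- Event rate 7.0% (Approach, Aim 1). It reproduces: 4,210 / 60,270 = 6.99%.
- About 300 patients per monthly list over 3 months, so about 900 list places; 172 per group (Approach, Aim 2).
- Benchmark detection 15% to 25%, and 40% in the existing program (Existing Services).

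The plan gives no sample size or power for adenoma detection. Its power statement concerns screening completion and is not affected here.

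**Assumptions**
- The earlier model's performance carries over.
- The flag uses that operating point.
- List places are distinct patients.
- Controls have the population mix.
- Other covariates remove none of the difference.
- Navigation has no effect on detection at a given risk.

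**Step 1: yield by flag at 7.0%**
- Flagged share = 0.44 × 0.07 + 0.10 × 0.93 = 0.0308 + 0.0930 = 12.4%.
- Yield if flagged = 0.0308 / 0.1238 = 24.9%.
- Yield if unflagged = (0.56 × 0.07) / 0.8762 = 0.0392 / 0.8762 = 4.5%.
- Flagged on the lists = 0.1238 × 900 ≈ 111.

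**Step 2: analysed participants are a prioritised subset.** Suppose half (56) or all (111) of the flagged patients are among the 172. Expected yield = f × 24.9% + (1 − f) × 4.5%, where f is the flagged share.

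| Flagged of 172 | f | Yield | Controls | Odds ratio |
|---|---|---|---|---|
| 56 | 33% | 11.1% | 7.0% | 1.66 |
| 111 | 65% | 17.6% | 7.0% | 2.85 |

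At 25% prevalence, flagged and unflagged yields are 59.5% and 17.2%. The same two flagged shares then give 30.9% and 44.5% against 25% (odds ratios 1.34 and 2.40).

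If the planned covariates removed half of the shift (assumed), the 7.0% case becomes 7.0 + 4.1/2 ≈ 9.1% and 7.0 + 10.6/2 = 12.3%.

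**Step 3: whole list analysed, detection counted among completers.** Control completion is taken as unrelated to risk, so the control rate stays at prevalence.
- Completion 60% flagged, 40% unflagged: (0.0308 × 0.6 + 0.0392 × 0.4) / (0.1238 × 0.6 + 0.8762 × 0.4) = 0.03416 / 0.42476 = 8.0%, or +1.0 point.
- Completion 60% flagged, 20% unflagged: 0.02632 / 0.24952 = 10.5%, or +3.5 points.
- At 40% prevalence the same two patterns give +3.6 and +11.1 points.

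**Step 4: why the denominator matters.** In the 60%/20% pattern at 7.0%, detections per listed patient are 2.6%. Controls completing at 40% would have 0.40 × 7.0% = 2.8%. The rate among completers rises while detections per listed patient fall slightly.

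**The case against.** The strongest objection is that targeting is the intervention. Aim 2 sets out to learn whether algorithm-informed navigation identifies more adenomas and cancers, so reaching higher-yield patients first is an intended mechanism. This stands, and it limits the remedy: matching a prioritised subset to controls of equal score, as the only analysis, would remove the targeting effect. What the objection does not supply is a way to tell targeting from better detection at a given risk.

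Second, the cohort is defined by zip code, practice and an uncompleted order, and the analysis is by intention to treat. If every listed patient is analysed, the flagged share should be similar in both periods. This also stands, and only the smaller shift in step 3 remains.

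Several stronger readings are tempting, but the documents do not support them:
- *The score is excluded from the matching.* The matching variables are not itemised, so this is silence. Only the outcome model is listed, and it lacks the score.
- *The score is wholly unadjusted.* Age, gender and comorbidity are score inputs and are in the model, and Aim 1 counts anemia as a comorbidity.
- *Odds ratios of 1.7 to 2.9 are the expected bias.* They need a prioritised subset. The upper end needs all 111 flagged patients to be analysed, although the plan assumes 50% dropout or refusal. Controls may also differ from the population mix, since age and prior screening are already used to stratify risk.
- *The reported performance describes the Aim 2 score.* It comes from an earlier model in an unselected cohort. The model will be retrained, and the clinics' views may lead to a CRC-only version.

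This is also a feasibility study, powered only for screening completion. That bears on priority; it does not remove the ambiguity in a co-primary outcome.

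**Conclusion.** The concern holds in a limited form. The plan compares adenoma detection between a period with risk-ranked outreach and one without, does not say that controls will be scored, and lists an outcome model that omits the score. A higher detection rate could therefore reflect case mix, and the planned analysis could not separate that from a navigation effect at a given risk.

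The size depends on who is analysed. For a prioritised subset with 33% to 65% flagged, the illustration gives 11.1% to 17.6% against 7.0%. For the whole list with detection among completers, it gives about +1 to +11 points across the assumed prevalences and completion patterns. Adjustment for shared inputs would shrink these figures. If completion also does not differ by risk, the gain from scoring is mainly balance and precision.

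A reader might infer that any observed rise would be spurious. The documents do not support that: a higher overall yield may be a genuine result of the program. The change is worth making because it is cheap and lets both questions be answered.

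**What to change.** 1. Run the same locked algorithm, with the same flag definition, on all historical controls, using only EHR data available at the equivalent list date.
2. Define the intention-to-treat comparison as every listed patient in the intervention period against all eligible controls.
3. For that whole-list comparison, include predicted risk in the propensity score and in the outcome models, itemise the other matching variables, and tabulate balance on the score.
4. Report adenoma detection overall, both per listed patient and per completed colonoscopy, and within flagged and unflagged strata. The overall result shows what the program achieves with targeting; the strata show navigation at a given risk.
5. State that score-matching of a prioritised subset does not replace the overall comparison.

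The cost is one batch scoring run, one added covariate and a few tables. Outcomes already come from routine EHR records. Controls with sparse EHR data will need a stated rule for missing predictors.

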Outcome. The primary outcome will be biopsy-proven CRC or adenoma, based on (1) diagnostic or procedural codes for CRC or adenoma using previously published administrative code mappings^{14,15}; and (2) internal datasets on Adenoma Detection Rate (ADR), generated by the Data Analytics Center using Provation and Clarity pathology data. Preliminary data suggest that 4,210 cases of CRC or adenomas exist in our cohort.

Predictors. We will use PennChart Clarity data from the 6 months prior to the colonoscopy as predictors in the model. Predictors will be adapted from prior literature and will include demographic (e.g. age, gender, EtOH history), comorbidity (e.g. anemia, inflammatory bowel disease), laboratory (e.g. hemoglobin, BUN), utilization (e.g. prior colonoscopy orders), and socioeconomic (e.g. area-level income and education) data.^{1,11,12} Additionally, we will use the EPIC social determinants of health tool to extract features such as income, education level, and homelessness that may be associated with CRC risk. .

Modelling strategy. We will compare the cross-validation predicted performance of several ML strategies, including logistic regression, random forest, gradient boosting, and recurrent neural networks, to identify the model with optimal predictive performance. We will report algorithm performance on the hold-out validation set, specifically testing for performance differences between the algorithms. Finally, we will compare performance of the best ML algorithm against an existing PennChart risk stratification model that uses only age and prior colorectal cancer screening utilization as predictors.

Performance metrics. Primary performance metrics will include area under the receiver operating characteristic curve (AUC), area under the precision-recall curve (AUPRC), and sensitivity.

Limitations. Administrative codes and internal ADR data may underestimate the true outcome rate, although the number of cases and event rate (7.0%) should still allow adequate model development.

Aim 2. Pilot testing of ML-facilitated colon cancer screening navigation

Study Design. Prospective cohort study with 3-month enrollment period and 3-month follow-up.

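### The historical control window has no stated months or index date, and calendar month is neither matched nor modelled, so a seasonal gap in screening completion could inflate or hide the intervention effect

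*Combined protocol and SAP*

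**What the plan says.** All of this is in the combined protocol and SAP.

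- **Approach, Aim 2, Study Design:** "Prospective cohort study with 3-month enrollment period and 3-month follow-up". The calendar months are not given in the text.
- **Aim 2, Outcome:** "The co-primary outcomes, measured within 3 months of enrollment". No corresponding start date is defined for a control.
- **Aim 2, Analysis Plan:** the comparator is a set of historical controls "from the same clinics in the year prior". Matched cohorts are formed by "propensity score matching using clinical and sociodemographic characteristics", and the logistic regression is "adjusted for age, gender, comorbidity, and area-level socioeconomic status". Neither list names month, season or calendar time.
- **Specific Aims, Aim 2:** outcomes are evaluated "compared to historical rates prior to the intervention", again without a window.
- **Aim 2, Statistical Power:** 344 participants, 172 per group, for a rise in completion from 40% to 60% at two-sided 0.05.
- **Aim 2, Intervention:** a monthly list of about 300 patients, with navigation staff rising from 1.5 to 2.5 FTE.

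**The concern.** The comparison is not randomised, so its credibility rests on how the controls are chosen. Enrolment takes one quarter, and all intervention outcomes fall within about six months (3 of enrolment plus 3 of follow-up). The control period is described only by year. If colonoscopy or FIT completion varies over the year, a cohort from one quarter and controls from a longer span have different expected completion rates even when navigation does nothing. No listed matching variable or covariate would remove that difference.

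The missing control index date adds to this. A control needs a defined day on which a 3-month outcome window opens, and that day also decides which season the control represents. If it is left open, the window could be settled after outcomes are known.

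The Work plan section says the results will support a grant application for a cluster-randomised trial, so a biased estimate could carry into that trial's planning.

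**Working it through.** **Inputs from the documents:** control completion 40%; intervention completion 60%; n = 172 per group; two-sided alpha 0.05; about 300 patients per monthly list; 3 months of enrolment.

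**Assumed inputs:** the seasonal gap s, meaning the enrolment quarter's completion rate minus the control-period average with no intervention effect. The documents give no value, so a range is shown. The calculation treats the groups as independent, as an approximation to the matched analysis.

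**Formula.** For rates p1 (control) and p2 (intervention), d = p2 - p1 and pbar = (p1 + p2)/2:

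- SE0 = sqrt[2 pbar(1 - pbar)/n]
- SE1 = sqrt[(p1(1 - p1) + p2(1 - p2))/n]
- P(reject) = Phi[(d - 1.96 SE0)/SE1] + Phi[(-d - 1.96 SE0)/SE1]

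**Step 1: the plan's own power.** With p1 = 0.40, p2 = 0.60 and n = 172: SE0 = 0.0539, SE1 = 0.0528, (0.20 - 1.96 x 0.0539)/0.0528 = 1.79, power 96.3%. The stated figure of more than 90% is therefore met if all 172 per group are analysed. If the plan's 50% dropout or refusal means 86 per group are analysed, power is 75.1%. That discrepancy is a separate matter and the present point does not depend on it.

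**Step 2: false positives under a seasonal gap, no true effect.** Set p1 = 0.40 and p2 = 0.40 + s, with n = 172.

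- s = 0: 0.025 + 0.025 = 5.0%
- s = 3 pp: SE0 = SE1 = 0.0531; Phi(-1.40) + Phi(-2.53) = 0.081 + 0.006 = 8.7%
- s = 5 pp: SE0 = 0.0533, SE1 = 0.0532; Phi(-1.02) + Phi(-2.90) = 0.153 + 0.002 = 15.5%

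Over a wider range, s = 2 pp gives 6.6%, 8 pp gives 32.1% and 10 pp gives 46.2%.

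**Step 3: lost power when the enrolment quarter is a poor one.** With a true effect of 20 pp and s = -5 pp, the comparison is 40% vs 55%: SE0 = 0.0538, SE1 = 0.0532, (0.15 - 1.96 x 0.0538)/0.0532 = 0.84, power 79.8%, down from 96.3%. With s = -10 pp it is 46.2%. Both are before any dropout.

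**Step 4: what enters the estimate.** Suppose the enrolment quarter differs from the other three by D and controls are spread evenly over the year. The control average already contains a quarter of D, so the bias is 0.75 D. For example, D = 8 pp gives 6 pp. With same-month controls and a stable seasonal pattern, this term is zero.

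**Step 5: size of a same-month control pool.** If prior-year volume matched the planned lists (an assumption), three months give 3 x 300 = 900 listings, against 12 x 300 = 3,600 for a full year. Required controls are 172 at 1:1, 344 at 1:2 and 688 at 1:4. Eligibility looks back 6 months for an order, so one patient may appear on several lists. With complete overlap, the number of unique patients could be near 300: enough for 1:1, but not for 1:2.

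**The case against.** A reader might infer that the plan draws controls from all twelve months and that any seasonal difference is therefore counted as intervention effect. The documents do not support that as fact. A whole-year window is the natural reading of the phrase, but the same quarter one year earlier also fits it. What can be shown is that the window is undefined. Even under the whole-year reading, only the gap between the enrolment quarter and the control-period average enters, and it may mask an effect as easily as create one.

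Other objections also have force:

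- **No seasonality is documented.** The 3 to 5 pp range shows what a gap of that size would do, not that one is likely. The targeted effect, 20 pp, is much larger.
- **A larger analysed sample would make the false-positive rate look worse.** One could apply the calculation to all 900 or so listings per group, but the plan states 172 per group. Using every listing would also leave no reserve for matching from a same-month pool.
- **The control pool may be small.** About 300 per month describes the revised list, which includes Family Medicine practices that the Patients and clinics served section presents as an expansion. Prior-year volume is not stated, so generous matching ratios cannot be promised.
- **Same-month controls can be further away in time.** If the window means the preceding 12 months, its midpoint is about 6 + 1.5 = 7.5 months before mid-enrolment, against about 12 months for same-month controls. The protocol describes a screening disparity that is widening, so time trends matter too.
- **This is a one-year feasibility study.** That limits how much weight its effectiveness estimate should carry.

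These points narrow the concern without removing it. The window is undefined, calendar month is unaccounted for under the whole-year reading, and a full-year sensitivity analysis answers the point about distance in time.

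**Conclusion.** The point holds in a limited form. The plan defines neither the control months nor a control index date, and it names calendar month in neither the matching nor the model. If controls span a whole year, a seasonal gap enters the effect estimate with either sign. At the planned 172 per group and a 40% base rate, an assumed gap of 3 to 5 pp moves the false-positive rate from 5% to about 9-16%, and an adverse 5 pp gap moves power from about 96% to 80% before dropout. If the sponsor already intends same-month controls, this seasonal term is absent and only the wording is missing. Whether completion at these clinics is seasonal cannot be judged from the documents. Season is one time-related confounder that the analysis can still address; the documents do not establish that it is the main one. The change should be made because the bias is avoidable at low cost, not because it has been shown to exist.

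**What to change.** Add to the Aim 2 Analysis Plan:

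1. Give each historical control an index date equivalent to entry on the navigation list (the date on which the patient would first have met the listing criteria), with the same 3-month outcome window.
2. Draw controls from the same three calendar months one year earlier, or match exactly on calendar month of listing.
3. Keep the full preceding-year pool as a sensitivity analysis, and report both estimates.
4. Plan 1:1 matching on unique patients. Use a higher ratio only if the count of unique same-month patients allows it.

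The cost is a few sentences of text and a smaller control pool: at most about 900 listings if prior-year volume was similar, and fewer unique patients if listings repeat. Outcomes already come from routine EHR records, so the change should need no new data collection. It does not remove year-to-year change, such as the staffing increase from 1.5 to 2.5 FTE or the addition of Family Medicine practices, and the report should say so.
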